Doses will be escalated in the standard 3 + 3 fashion, starting with 5 x 10^9 colony forming units (CFU) to a maximum dose level of 1 x 10^{10} CFU. Dose cohorts of 3 subjects each will be treated. In the absence of dose-limiting toxicity (DLT) as defined in Section 6.1 Dose Limiting Toxicity assessed during the first treatment cycle, the dose will be escalated to the next dose level for the next 3 subjects. If DLT is seen in 1 of 3 subjects, another 3 subjects will be treated at that same dose. If DLT is seen in 2 of 6 subjects, then that dose level will be considered maximum tolerated dose (MTD) and the previous dose level will be selected as the recommended Phase 2 dose (RP2D). The RP2D will be selected based on an observed DLT rate of < 33%.

Treatment cycles can be repeated at the RP2D (or less) for an individual subject until a discontinuation criterion is met. Discontinuation criteria include documented disease progression, intolerable side effects not resolved with dose reduction or change in premedications or the subject completes 1 cycle of treatment post observation of complete response (CR) per RECIST 1.1 and immune-related RECIST criteria (irCR).

Sponsor:	Name of Finished Product:	Type of Treatment:
Advaxis, Inc.	ADXS11-001	Lm-LLO Immunotherapy

Further assessment of the RP2D level may be explored in an expansion cohort in subjects with persistent, metastatic, or recurrent carcinoma of the cervix who have failed conventional therapy to evaluate the safety and clinical activity of ADXS11-001. Treatment will continue for each subject until a discontinuation criterion is met. The end of treatment will be defined as 1 year after the last subject's first treatment or until that subject has met a discontinuation criterion. All subjects will be followed for adverse events (AEs) and serious adverse events (SAEs) from the time written informed consent is signed through the completion of the *Lm* surveillance period.

Safety will be assessed by comparing treatment-related AEs, changes in physical examinations, vital sign measurements, laboratory abnormalities and *Lm* surveillance monitoring.

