6 STUDY DESIGN AND TREATMENT PLAN

In this Phase 1, open-label, multi-center study, subjects with persistent, metastatic or recurrent squamous cell or non-squamous cell carcinoma, adenosquamous carcinoma, or adenocarcinoma of the cervix who have failed conventional therapy will receive the highest dose tolerated of ADXS11-001 infused intravenously (IV)

(± 10 minutes) with overall infusion volume of 250 mL on Day 1 of Weeks 1, 4, 7, and 10 of each 12-week cycle. Subjects must complete the prophylactic regimen at least prior to each ADXS11-001 infusion (as noted in Section 11.1) to mitigate and manage the potential immune response seen with immunotherapy administration.

Subjects who experience a DLT during the dose escalation portion of the study or experience events described as a DLT in any subsequent treatment cycle will be discontinued from study treatment. However, if the subject who experienced a DLT shows significant response to ADXS11-001, they may be eligible to receive ADXS11-001 at a lower dose level for subsequent doses and cycles following discussion and agreement between the Investigator and Sponsor. See Section 6.1 Dose Limiting Toxicity Criteria for definition of DLT.

The treatment to be used in this trial is outlined below in Table 4. Trial treatment should begin on the day of randomization or as close as possible to the date on which the treatment level is allocated/assigned.

Details on the dose calculation, preparation and administration are provided in the Pharmacy Manual.

Table 4 Trial Treatment

[figure not shown]
Dose Level	ADX11-001	Schedule
1	5 x 10 ⁹ CFU	Q3wks
2	$1 \times 10^{10} \text{CFU}$	Q3wks
-1	$1 \times 10^9 \text{CFU}$	Q3wks

ADXS11-001 will be given as a 3 weeks in repeating 12-week cycles

250 mL IV infusion every

A standard 3 + 3 design will be used in the dose escalation portion of the study. ADXS11-001 will be administered in sequential cohorts of 3-6 subjects, with a minimum of 48 hours between initial dosing for each of the first 3 subjects treated at each dose level. The first cohort will enroll a minimum of 3 subjects, according to a standard 3 + 3 design shown schematically in Figure 1.

Figure 1 3+3 Design Schematic

- Subjects in the first cohort will receive a dose of ADXS11-001 5 x 10⁹ CFU (Dose Level 1).
- If no DLTs are experienced in the 28 day DLT observation period at Dose Level 1, the next dose level of ADXS11-001 1 x 10¹⁰ CFU (Dose Level 2) will be explored.

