- If 1 DLT is experienced at Dose Level 2 (ADXS1-001 1 x 10¹⁰ CFU), then 3 additional subjects will be enrolled at that same dose level. If there is 1 DLT among the 6 subjects, then the Dose Level 2 may be identified as the RP2D and will be expanded to further define safety and efficacy.
- If \geq 2 DLTs are observed within 28 days of dosing for subjects in the first dose cohort, the starting dose of ADXS11-001 will be de-escalated to 1 x 10⁹ CFU and a dose de-escalation cohort may be enrolled (Dose Level -1).

All decisions regarding dose level escalation or de-escalation will be guided by the 3 + 3 study design and will be made by the Sponsor in consultation with the Investigator(s).

The RP2D will be selected based on an observed DLT rate of <33%. The Sponsor reserves the right to expand the number of subjects in each of the cohorts to better evaluate safety and tolerability. Cohorts will be expanded in groups of 3 subjects.

Following identification of the RP2D, additional subjects may be enrolled into the expansion cohort to allow approximately 15 subjects to be treated at that dose level. All subjects in the Dose Expansion Cohort may be enrolled simultaneously.

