6.1 Dose Limiting Toxicity Criteria

DLT will be evaluated during the first 28 days of the first cycle during the dose escalation portion of the trial. All toxicities will be graded using CTCAE v 4.03. The occurrence of any of the following toxicities will be considered a DLT, if judged by the Investigator to be possibly, probably or definitely related to therapy. Treatment modifications for DLT are shown in Table 11.

Hematologic:

- 1. Grade 4 hematologic toxicity.
- 2. Febrile Neutropenia, defined as absolute neutrophil count (ANC) < 1000/mm³ with a single temperature of >38.3° C (101° F) or a sustained temperature of >38° C (100.4° F) for more than 1 hour.
- 3. Grade 3 thrombocytopenia lasting >72 hours.
- 4. Grade 4 thrombocytopenia.

Non-Hematologic:

1. ≥Grade 3 non-hematologic toxicity, (excluding nausea, vomiting and/or diarrhea lasting <3 days and reversible with medical intervention).

- 2. Grade 3 non hematologic laboratory values, (excluding transient Grade 3 laboratory value abnormalities, hematologic and non-hematologic, reversible within 5 days and without necessity for medical intervention).
- 3. Listeremia: positive blood cultures(s) along with persistent (for 72 hours post dose) symptoms consistent with listeremia (e.g., fever and muscle aches, often preceded by diarrhea or other gastrointestinal symptoms).
- 4. \(\geq \) Grade 3 flu-like symptoms or cytokine release symptoms that persist for >24 hours after study treatment administration despite symptomatic treatment.

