11.6.1 Treatment Modification Guidelines

The dose of ADXS11-001 will not be modified (e.g., reduced or increased). However, treatment may be delayed or discontinued for drug related severe and life-threating toxicities, as shown below in Table 11.

Table 11 Treatment Delay/Discontinuation Guidelines for Drug-Related Adverse Events

Toxicity	Grade	Hold treatment	Timing for restarting treatment	Discontinue Treatment
	1,2,3	No	N/A	N/A
Hematologic	4	Yes	Toxicity resolves to ≤Grade 1 or baseline	Toxicity does not resolve to ≤Grade 1 or baseline within 12 weeks
	1	No	N/A	N/A
Non- hematologic, excluding cytokine release symptoms and DLTs	2-3	Yes	Toxicity resolves to ≤Grade 1	Toxicity not resolved to ≤Grade 1 within 12 weeks of last infusion ^a
	4	N/A	Permanent treatment discontinuation	Permanent Discontinuation from Treatment

^a With investigator and sponsor agreement, subjects with a non-hematologic AE (e.g. alopecia, neuropathy) still at grade 2 after 12 weeks, may continue treatment if only asymptomatic and controlled.

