13.6 Evaluating Adverse Events

An Investigator who is a qualified physician will evaluate all AEs according to the CTCAE v 4.03 (See Table 12). Any AE that changes CTCAE grade over the course of a given episode will have each change of grade recorded on the AE case report forms/worksheets. All AEs regardless of CTCAE grade must also be evaluated for seriousness.

Table 12 Evaluating Adverse Events

V4.03 CTCAE Grading	Grade 1	Mild; asymptomatic or mid symptoms; clinical or diagnostic observations only; intervention not indicated.			
	Grade 2	Moderate; minimal, local or noninvasive intervention indicated; limiting age-appropriate instrumental ADL.			
	Grade 3	Severe or medically significant but not immediately life-threatening; hospitalization or prolongation or hospitalization indicated; disabling; limiting self-care ADL.			
	Grade 4	Life threatening consequences; urgent intervention indicated.			
	Grade 5	Death related to AE			
Seriousness	A serious adv	erse event is any adverse event occurring at any dose or during any use of Advaxis product that:			
	†Results in de	eath; or			
	†Is life threatening; or places the subject, in the view of the investigator, at immediate risk of death from the event as it occurred (Note: This does not include an adverse event that, had it occurred in a more severe form, might have caused death.); or				
	†Results in a persistent or significant disability/incapacity (substantial disruption of one's ability to conduct normal life functions); or				
	†Results in or prolongs an existing inpatient hospitalization (hospitalization is defined as an inpatient admission, regardless of length of stay, even if the hospitalization is a precautionary measure for continued observation. (Note: Hospitalization [including hospitalization for an elective procedure] for a preexisting condition which has not worsened does not constitute a serious adverse event.); or				
	†Is a congenital anomaly/birth defect (in offspring of subject taking the product regardless of time to diagnosis);or				
	Is a new cancer; (that is not a condition of the study) or				
	Is an overdose (whether accidental or intentional). Any adverse event associated with an overdose is considered a serious adverse event. An overdose that is not associated with an adverse event is considered a non-serious event of clinical interest and must be reported within 24 hours.				

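### The gastrointestinal exclusion in DLT item 1 has no grade limit, so a drug-related Grade 4 diarrhea that permanently ends treatment is scored as no DLT

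*Combined protocol and SAP*

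**What the plan says.** Section 6.1 lists the DLT criteria for the first 28 days of cycle 1, for events judged at least possibly related. Non-hematologic item 1 reads "≥Grade 3 non-hematologic toxicity, (excluding nausea, vomiting and/or diarrhea lasting <3 days and reversible with medical intervention"). Item 2, on laboratory values, also has an exclusion, but that one names its grade: "excluding transient Grade 3 laboratory value abnormalities".

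Table 12 (section 13.6) describes Grade 4 as "Life threatening consequences; urgent intervention indicated".

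Table 11 (section 11.6.1) has a row for drug-related non-hematologic events, "excluding cytokine release symptoms and DLTs". The action at Grade 4 is "Permanent Discontinuation from Treatment".

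The dose decisions are stated in DLT counts:
- Section 6: "If no DLTs are experienced in the 28 day DLT observation period at Dose Level 1, the next dose level of ADXS11-001" is explored.
- Synopsis: "If DLT is seen in 1 of 3 subjects, another 3 subjects will be treated at that same dose". At 2 of 6, the previous dose level becomes the RP2D.
- Section 6: "The RP2D will be selected based on an observed DLT rate of <33" per cent, and 1 DLT among 6 at Dose Level 2 is acceptable.

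**The concern.** An exclusion of this kind is meant to keep brief, manageable gastrointestinal events from stopping escalation. Item 1 starts at Grade 3 with no ceiling, and its exclusion has no ceiling either, so it also removes life-threatening events that respond to treatment within 3 days. Item 2 shows that a grade limit could have been written here too.

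The subject-level and dose-level rules then disagree. Such a subject leaves treatment for good under Table 11. That is stricter than the handling of a DLT, since sections 6 and 11.6.2 let a responding subject with a DLT resume at a lower dose. Yet for the dose decision the event counts as nothing. The two planned levels are 5 and 10 times the 1 x 10^9 CFU that section 3.5 calls the standard dose, and a level can clear on three subjects, so one unscored event can settle the decision.

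**Working it through.** **Tracing one event.** Take a related Grade 4 diarrhea on study day 2, reversed with treatment in under 3 days, with no other toxicity.

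| Rule | Result |
|---|---|
| 6.1 item 1 | Excluded: under 3 days and reversible |
| 6.1 item 2 | Not met: laboratory values only |
| 6.1 item 3 | Not met: needs a positive blood culture |
| 6.1 item 4 | Not met as a rule: flu-like or cytokine release symptoms beyond 24 hours; the lists in 11.1, 11.4.1 and 11.6 include nausea and vomiting but not diarrhea |
| Table 11, Grade 4 | Permanent discontinuation |

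The event is not a DLT. The gap is narrower for vomiting: Grade 3 or higher vomiting attributed to cytokine release and lasting more than 24 hours is a DLT under item 4, and cytokine release symptoms are outside this Table 11 row. Fatal or non-reversible events remain DLTs under item 1.

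**The plan's own figure.** Section 14.3 gives 6-12 subjects for escalation. Two levels of 3 or 6 subjects each give a minimum of 3 + 3 = 6 and a maximum of 6 + 6 = 12. The figure reproduces and does not depend on this point.

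**Effect on the decision when the event occurs.**
- Dose Level 1, no other DLT: as written 0/3, escalate. Counted: 1/3, treat three more.
- Dose Level 2, one other DLT among six: as written 1/6 = 16.7%, acceptable as RP2D. Counted: 2/6 = 33.3%, not below 33%, so the previous level is the RP2D.

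If the event is scored as 1/3, the level clears only when the next three subjects have no DLT, with probability (1 - b)^3 for a DLT rate b (assumed):
- b = 10%: 0.9^3 = 72.9%
- b = 20%: 0.8^3 = 51.2%
- b = 30%: 0.7^3 = 34.3%

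As written, the level clears on the first three subjects.

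**Effect averaged over how often the event occurs.** The documents give no rate, so p below is assumed. The only severe-event rate visible is about 1% for Grade 3-4 hypotension (section 11.4.1).

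The chance of at least one such event among three subjects is 1 - (1 - p)^3: 1.5% at p = 0.5%, 3.0% at p = 1%, 8.7% at p = 3%.

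A level clears at 0/3, or at 1/3 followed by 0/3:

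P(clear) = (1 - q)^3 + 3q(1 - q)^2 (1 - q)^3

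Here q = b when the events are ignored, and q = 1 - (1 - b)(1 - p) when they are counted, treating them as independent of other DLTs. For b = 20% and p = 1%, q = 1 - 0.80 x 0.99 = 0.208.

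| b | p | Ignored | Counted | Difference (points) |
|---|---|---|---|---|
| 20% | 0.5% | 70.9% | 70.0% | 0.9 |
| 20% | 1% | 70.9% | 69.1% | 1.7 |
| 20% | 3% | 70.9% | 65.6% | 5.2 |
| 10% | 1% | 90.6% | 89.1% | 1.5 |
| 30% | 1% | 49.4% | 48.0% | 1.4 |

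Differences are taken before rounding (for example 0.7086 - 0.6912 = 0.0174).

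**The case against.** The strongest reply is that the event is very narrow and cannot pass unnoticed. It must be life-threatening, related, within 28 days, over in under 3 days, and free of any other DLT in the same subject. Accompanying Grade 3 hypotension would count under item 1, and an accompanying Grade 3 laboratory abnormality needing treatment would count under item 2. A life-threatening event is an SAE, reportable within 24 hours. Section 11.8.2 allows the study to be suspended after any Grade 4 toxicity. Section 6 leaves dose decisions to the sponsor in consultation with investigators and lets cohorts be expanded, and section 14.3 ties escalation enrolment to AEs as well as DLTs. Table 11 applies in every cycle, so permanent discontinuation does not by itself make an event a DLT. The cytokine release list is also open-ended, so an investigator might place diarrhea under item 4.

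Much of this is fair. It makes an unsafe escalation less likely, and if these events cluster with other DLTs in the same subject, the averaged differences above are too large. But every safeguard is discretionary or depends on a second event, and none makes the diarrhea a DLT. The item 4 route still misses anything lasting 24 hours or less. The stated triggers for escalation and the RP2D remain DLT counts, and applied as written they give 0/3 or 1/6. The absence of diarrhea from the expected events in section 11.6 is weak evidence on frequency, because the safety summary in section 3.4.1 is not shown; section 6.1 itself names diarrhea as a possible precursor of listeremia.

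**Conclusion.** The criterion is wrong as written and should be corrected. That rests on the text alone and needs no assumed rate: a related Grade 4 diarrhea meeting both conditions is not a DLT, while Table 11 ends that subject's treatment. Per event the consequence is large, since it can change whether Dose Level 1 clears on three subjects or whether Dose Level 2 qualifies as the RP2D. Averaged over an assumed 1% event rate it is small, about 1.4 to 1.7 percentage points in the chance of clearing a level for DLT rates of 10% to 30%, assuming independence from other DLTs. Because the true rate is unknown from these documents, those averages are illustrations and not estimates.

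**What to change.** In section 6.1, non-hematologic item 1, insert the words Grade 3 before nausea, so that the exclusion covers only Grade 3 nausea, vomiting and/or diarrhea that last under 3 days and are reversible with treatment. Any related Grade 4 vomiting or diarrhea in the 28-day window then counts as a DLT, in line with Table 11, and brief Grade 3 events stay excluded as intended.

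The cost is one grade limit at the next amendment, with no added data collection. The observed DLT rate may be slightly higher, and a cohort may occasionally need three more subjects, still within the planned 6-12.

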7 INVESTIGATIONAL CENTERS

This is a multi-center study.

7.1 Subject Accrual

Subjects will be recruited from a population of patients with recurrent, metastatic, or persistent squamous and non-squamous cell carcinoma, adenosquamous or adenocarcinoma of the cervix. The subject's medical record, including the most recent treatment, will be reviewed by the Investigator to determine the suitability of the subject for the study.

7.2 Subject Enrollment

Each subject who gave signed informed consent and was screened for admission into the study will be assigned a unique sequential number that also includes their study site. The identification number and the subject's initials should be recorded on all case report forms (CRFs) and correspondence regarding the subject following study registration.

7.3 Subject Study Participation

Each subject may participate in the study for up to 5 years from the time informed consent is signed through the final study contact. This includes a study treatment phase (~24 months), a 3-year post-ADXS11-001 treatment *Lm* surveillance period which includes a prophylactic oral antibiotic administration period (6 months) and *Lm* surveillance monitoring approximately every 3 months for 3 years. It is expected that a subject will participate in the study until the completion of the full 3-year *Lm* surveillance period. However, following the completion of the 6 month oral antibiotic treatment, a subject will be eligible to participate in other investigational clinical studies.

8 STUDY EVALUATION

The key study procedures and the frequency of their occurrences are outlined in Table 5.

Table 5 Schedule of Events

	Screening ¹	12 Week Treatment Cycle ²												End of		
Study Procedure	Days -28 to 0		k 1 ⁴ I Post	Wk 2	Wk 3 ⁵	Wk 4	Wk 5	Wk 6 ⁵	Wk 7	Wk 8	Wk 95	Wk 10	Wk 11	Wk 12	Therapy ⁶	Follow-Up
Administrative Procedures	1 20 00 0	1	1 1 000									10				
Informed consent ⁷	X															
Eligibility Criteria	X	X														
Demographics/Medical History	X															
Surgical History ⁸	X															
Prior Cancer History	X															
Prior/Concomitant Medications	X	X	X			X			X			X			X	
Non Drug Treatment/Procedures ⁹	X	X	X			X			X			X			X	
Prophylactic Medication ¹⁰		X				X			X			X				
ADXS11-001 Administration ¹¹			X			X			X			X				
Dispense/Prescribe Oral			X			X			X			X			X	X
Prophylactic Antibiotics ¹²																
Phone Call ³																X
Clinical Procedures/Assessments																
Review Adverse Events (AE) ¹³	X	X	X			X			X			X			X	X
Physical exam ¹⁴	X	X				X			X			X			X	
Vital Signs ¹⁵	X	X	X			X			X			X			X	
ECOG Performance Status	X	X				X			X			X			X	
Laboratory Procedures/Assessme	ents ¹⁶															
CBC with Differential	X	X				X			X			X			X	
Serum Chemistry Panel	X	X				X			X			X			X	
Coagulation Profile ¹⁷	X															
Urine Dipstick	X	X				X			X			X			X	
Pregnancy Test ¹⁸	X	X				X			X			X			X	
Lm Surveillance Monitoring ¹⁹																X
Efficacy Measurements/Correlati	ive Studies															
Tumor Imaging ²⁰	X													X	X	
Immune monitoring/T Cell ²¹		X			X	X		X	X		X	X		X		
Cytokines ²²		X	X			X			X			X				

Screening procedures, including tumor evaluations will be performed within 28 days prior to first dose of study treatment to determine study eligibility.

² Repeating 12-week treatment cycles.

- Safety Follow-Up will be conducted via a telephone call 30 days (± 5 days) after the last ADXS11-001 infusion to confirm the resolution of any new or ongoing AEs or SAEs.
- ⁴ At every ADXS11-001 infusion, the indicated pre and post procedures will be performed.
- Week 3, Week 6 and Week 9 visits will be performed during Cycle 1 only. After cycle 1, these visits are not required.
- ⁶ End of Therapy is not a visit. Assessments noted here must be completed upon the decision to discontinue a subject from study treatment.
- Informed Consent must be obtained prior to conducting screening evaluations.
- Documentation of non-cancer surgeries, including, but not limited to artificial (prosthetic) joints, implants and/or devices, such as port/stent implant placed prior to study enrollment.
- Documentation of any on-study non-drug treatment and surgical procedures, including but not limited to artificial (prosthetic) joints, implants and/or devices.
- The pretreatment prophylactic regimen will be administered prior to and completed at least before each ADXS11-001 infusion.
- ADXS11-001 may be administered ± 7 days within Day 1 of each scheduled infusion. ADXS11-001 should not be administered less than 2 weeks apart without Sponsor approval.
- All subjects will receive a 7-day course of oral antibiotic therapy starting 72 hours after administration of ADXS11-001. All subjects will also receive an additional 6-month oral antibiotic course to be initiated 72 hours following the last dose of study treatment or upon discontinuation of study treatment.
- AEs and SAEs will be assessed from the time Informed Consent is obtained through the completion of the *Lm* surveillance period. All AE/SAEs will be followed through resolution. All AEs/SAEs experienced during this period must be recorded on the eCRF.
- Physical Examinations are to be completed prior to the ADXS11-001 administration to confirm safety criteria for study drug administration are met. PEs may be performed more frequently, as clinically indicated. Height will be measured at screening only. Weight will be collected prior to each ADXS11-001 infusion.
- Monitor vital signs every following the completion of every ADXS11-001 infusion.
- All laboratory procedures are to be completed and assessed by the investigator within 3 days prior to the administration of study treatment to confirm safety criteria for study treatment administration are met.
- 17 Coagulation profile will be assessed at screening only.
- A pregnancy tests must be performed within 72 hours prior to each ADXS11-001 infusion for female subjects of childbearing potential or less than 1 year postmenopausal. If the urine test is positive or cannot be confirmed as negative, a serum pregnancy test will be required.
- 19 Lm surveillance will include routine monitoring of CBC, CMP (including CRP, ESR) and blood cultures. Following completion of study treatment all assessments will be performed every 3 months (±2 weeks) for 3 years beginning 3 months after the subject's last dose of study treatment.
- Baseline tumor imaging and assessments must be performed within 28 days prior to the first ADXS11-001 infusion in the first study cycle. Subsequent tumor imaging and assessments will be conducted at Week 12 (±1 week) for the duration of study participation. Apparent progression within the first 12 weeks, not accompanied by clinical deterioration, should be confirmed ≥4 weeks later.
- Immune monitoring/T-cell samples will be collected immediately prior to each ADXS11-001 infusion (Day 1 of Weeks 1, 4, 7, and 10) and between 11-14 days after every ADXS11-001 infusion in Cycle 1 only.
- Cytokine samples will be collected **in Cycle 1 only** at 3 time points immediately prior to each ADXS11-001 infusion and 2 hours and 4 hours post infusion (±15 minutes- Day 1 of Weeks 1, 4, 7, and 10).

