8.3 Study Cycle Evaluation

Baseline imaging studies and tumor assessments must be performed within 28 days prior to the first ADXS11-001 infusion in the first Treatment Period. Subsequent assessments will be conducted at Week 12 in Cycle 1, followed by assessment every 12 weeks (± 1 week) thereafter. Apparent progression within the first 12 weeks not accompanied by clinical deterioration, should be confirmed 3 to 4 weeks later.

Blood samples for immune monitoring and cytokine/chemokine analysis should be collected per schedule in Cycle 1 only (See Section 8.1 Study Procedures).

A physical examination, an ECOG Performance Status, vital sign measurements, hematology and chemistry profiles, and urinalysis will be performed prior to each study treatment infusion and at the end of therapy. Subjects will also be asked about the occurrence of any AEs and changes to concomitant medications.

Vital signs (including blood pressure, pulse rate, respiratory rate, and temperature) will be checked and recorded prior to administration of ADXS11-001 and following the infusion. Weight will be collected prior to each ADXS11-001 infusion.

A urine pregnancy test will be performed within 72 hours prior to each ADXS11-001 infusion and at the end of therapy for all women of childbearing potential.

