11.6 ADXS11-001 Toxicities and Treatment

Please refer to Section 3.4.1 for summary information on the ADXS11-001 AE profile.

ADXS11-001 is a live attenuated bioengineered nonpathogenic strain of Lm, and one that is known to stimulate a strong innate immune response characterized by high levels of cytokine release from immune cells into the general circulation. This pattern of side effects is consistent with other immunotherapy agents.

The most likely AEs associated with ADXS11-001 are comprised primarily of individual flu-like symptoms (e.g., fever, chills, body ache, and fatigue) or cytokine release symptoms (e.g., headache, nausea, vomiting, tachycardia, shortness of breath, hypotension and rash). The symptoms usually present within 2-4 hours after the completion of infusions and are often mild to moderate and transient in nature or respond quickly to symptomatic treatment. In rare instances they may last up to 24 hours. No cumulative or delayed toxicity has been observed.

Less likely AE's include increase heart rate, low blood pressure, muscle aches, headaches, allergic reaction, changes in blood chemistry, changes in blood counts, and short term changes in liver function.

Rare but serious AEs include high fever and difficulty breathing and hypotension.

, ADXS11-001 has a tropism for the liver. Transient asymptomatic elevations of ALT and alkaline phosphatase were observed after dosing in the Phase 1 trial without prophylactic medication administration. For that reason, subjects with significant liver disease are excluded, and particular attention is to be paid to hepatic abnormalities.

Please reference the ADXS11-001 IB for complete information regarding AEs.

During the time the subjects are at the study site, the infusion line will be left in place to administer parenteral drugs, should that be necessary. As described in Section 11, subjects will be pretreated to minimize side effects of the study agent. The Investigator should observe the subjects for signs of inflammation and/or infection, including unremitting fever or vomiting, that require more intense therapy, and to treat them appropriately. All such treatments are to be listed on the eCRF.

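### Laboratory DLTs are under-ascertained: the 28-day window holds at most one scheduled post-dose CBC/chemistry and none after infusion 2, and scheduled draws alone cannot settle the two laboratory duration clauses

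*Combined protocol and SAP*

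**What the plan says.** **Window.** Section 6.1: "DLT will be evaluated during the first 28 days of the first cycle during the dose escalation portion of the trial". Section 6 also uses 28 days. The Synopsis (Methodology) instead places DLT assessment in the first treatment cycle, and a cycle is 12 weeks.

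**Infusions.** Section 6 gives them "on Day 1 of Weeks 1, 4, 7, and 10 of each 12-week cycle", nominally Days 1, 22, 43 and 64. Two therefore fall inside 28 days. Table 5 allows each infusion to move by 7 days either way.

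**Safety labs.** The Table 5 footnote reads "All laboratory procedures are to be completed and assessed by the investigator within 3 days prior to the administration of study treatment", and the purpose it gives is to confirm that the subject may be dosed. Section 8.3 agrees: "hematology and chemistry profiles, and urinalysis will be performed prior to each study treatment infusion and at the end of therapy". Section 13.8 repeats the 3-day pre-dose rule. Table 5 marks CBC and chemistry at Screening, Week 1 pre-dose, Weeks 4, 7 and 10, and End of Therapy. It marks none after the Week 1 dose and none in Weeks 2, 3, 5 or 6. There are extra visits ("Week 3, Week 6 and Week 9 visits will be performed during Cycle 1 only"), but Table 5 marks only immune-monitoring blood there.

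**Criteria.** Section 6.1 lists eight DLT criteria. One is "Grade 3 thrombocytopenia lasting >72 hours". Another excludes transient Grade 3 laboratory changes that are "reversible within 5 days and without necessity for medical intervention".

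**The concern.** The laboratory schedule answers one question (may the next dose be given?), while the DLT rule asks another (did a laboratory toxicity occur after dosing, and how long did it last?). A silent abnormality that comes and goes between draws is never recorded. Section 11.6 makes silent events plausible: "Transient asymptomatic elevations of ALT and alkaline phosphatase were observed after dosing in the Phase 1 trial".

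The cohort decision turns on very small counts. One missed event changes 1 of 3 (enroll three more) into 0 of 3 (escalate). Missed events can only lower the count, so the error runs towards the higher dose and towards a recommended Phase 2 dose that looks safer than it is.

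**Working it through.** **1. The plan's own figures.** With 3 or 6 subjects at Level 1 and 3 or 6 at Level 2 or Level -1, the range is 3 + 3 = 6 to 6 + 6 = 12, which matches Section 14.3. The below-33% rule is consistent with the 3+3 design: 1/6 = 16.7% passes and 2/6 = 33.3% fails. The plan gives no figure for how completely DLTs are detected.

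**2. Visit arithmetic.** Lab day = infusion day minus 0 to 3.

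| Infusion 2 | Labs before infusion 2 | Earliest infusion 3 | Earliest next labs |
|---|---|---|---|
| Day 15 (-7) | Days 12-15 | Day 36 | Day 33 |
| Day 22 (nominal) | Days 19-22 | Day 36 | Day 33 (nominal Days 40-43) |
| Day 29 (+7) | Days 26-29 | Day 43 | Day 40 |

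In every case there is at most one post-dose draw by Day 28 and none after infusion 2. In the last row the single draw may itself miss the window. The exception is a subject who stops treatment early and has End of Therapy labs.

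**3. Criteria affected.** Five of the eight use CBC or chemistry values: all four hematologic criteria and the Grade 3 laboratory criterion. Grade 4 thrombocytopenia is already contained in Grade 4 hematologic toxicity, and febrile neutropenia presents with fever. That leaves three distinct criteria that can be met silently. Two of these carry a duration clause (over 72 hours; within 5 days). No section requires a repeat test timed to either limit. Table 11 does not hold treatment for hematologic Grades 1-3. Section 13.8 sends a laboratory abnormality to the AE page only if it is serious, interrupts or stops treatment, or needs corrective therapy. A Grade 3 platelet count before infusion 2 need not lead to a re-test.

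**4. Detection by the single draw.** Assume onset uniform over Days 2-28 (27 days) and a duration of d days. A draw on Day 22 catches the d onset days from 23 - d to 22, so detection = d/27:
- 4 days: 4/27 = 15%
- 6 days: 6/27 = 22%
- 10 days: 10/27 = 37%
- 14 days: 14/27 = 52%

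If onset is on Days 2-5 and duration is up to 14 days, the last abnormal day is at most 5 + 14 - 1 = 18, so a draw on Days 19-22 catches none. Onset on Days 23-28 is also never caught.

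**5. Effect on the 3+3 rule.** Let p be the true DLT rate, L the share that is laboratory-only and s the proportion of that share detected. Then q = p[(1 - L) + Ls], and P(level clears) = (1 - q)^3 + 3q(1 - q)^5. All inputs are assumptions.
- p = 0.40, all detected: q = 0.40; 0.216 + 0.093 = 0.309.
- L = 0.5, s = 0.15: q = 0.40 x 0.575 = 0.23; 0.457 + 0.187 = 0.643.
- L = 0.5, s = 0.50: q = 0.40 x 0.75 = 0.30; 0.343 + 0.151 = 0.494.

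| p | All detected | L = 0.25, s = 0.15 to 0.50 | L = 0.5, s = 0.15 to 0.50 |
|---|---|---|---|
| 0.33 | 43% | 58% to 52% | 73% to 61% |
| 0.40 | 31% | 46% to 40% | 64% to 49% |
| 0.50 | 17% | 32% to 25% | 52% to 35% |

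**The case against.** A reader might infer that the laboratory and duration-based DLT criteria cannot be applied at all, or that detection is close to zero. The documents do not support either reading.
- Grade 4 hematologic toxicity has no duration condition, so one value at the draw is enough.
- The flu-like/cytokine, gastrointestinal and listeremia time limits rest on symptoms, AE dates and cultures, not on CBC or chemistry.
- Grade 3 changes that reverse within 5 days without intervention are excluded by design, so missing those is no error.
- Near-zero detection holds only for early, short events or for onset after infusion 2.

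A reader might also treat the ALT and alkaline phosphatase rises as evidence of missed DLTs. Section 11.6 gives no grade for them and says they occurred without prophylactic medication, which subjects here are to receive. They show that silent laboratory effects are plausible, not that they reach DLT grade.

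Nor is a cohort decision fixed for Day 28. The plan sets an observation period but no decision date, and the Week 7 AE review can record an earlier onset.

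Several safeguards exist. Hepatic and renal criteria must be met before each later dose, so a persistent liver or renal abnormality should be found before infusion 2. Table 11 holds treatment for non-hematologic Grade 2-3 toxicity. Unscheduled visits are possible at the investigator's discretion. Escalation is a single step to a dose already tested in Phase 1, cohorts may be enlarged, and a Grade 4 event may suspend the study.

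These points narrow the concern and bound its consequences. They do not remove it: none requires a CBC or chemistry between infusion 2 and Day 28 or times a repeat to either limit, and retrospective AE review cannot recover a value that was never drawn.

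**Conclusion.** The concern holds in a limited form. In the 28-day window there is at most one scheduled post-dose CBC/chemistry and none after infusion 2. Asymptomatic laboratory DLTs are under-ascertained, with bias towards clearing a dose level. The 72-hour platelet clause and the 5-day reversibility clause cannot be determined from scheduled draws alone.

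The count of draws and the direction of the bias follow from the documents. The size does not: onset, duration and the laboratory-only share are not given, so the detection and clearing probabilities above are illustrations.

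The count also depends on the 28-day window. If the Synopsis wording governed, the Week 7 and Week 10 labs would fall inside the assessment period. Draws about 21 days apart would still not time a 72-hour or 5-day limit.

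**What to change.** For Cycle 1 of the escalation cohorts:

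- **(a) Week 3.** Add CBC with differential, chemistry and AE review to the existing visit, where blood is already taken. Under the assumptions of working step 4, draws on Days 15 and 22 together catch 8, 12, 17 and 21 of the 27 onset days for durations of 4, 6, 10 and 14 days: 30%, 44%, 63% and 78%, against 15%, 22%, 37% and 52% now. An event that resolves by about Day 11 is still missed.
- **(b) Timed re-tests.** Require a Grade 3 laboratory value found in the window to be re-tested when the clause can be decided: after 72 hours for platelets and at 5 days for the reversibility exclusion. Count it as a DLT if it is not re-tested. A platelet repeat within 72 hours cannot show a duration beyond 72 hours.
- **(c) Before each cohort decision.** Require a documented AE review covering every day through Day 28. Either obtain a CBC/chemistry after infusion 2 and by Day 28, or state how Week 6 labs count. Week 6 falls at about Days 33-36, after the window, so adding labs there does not by itself fill the gap.
- **(d) Reconcile** the Synopsis (DLTs assessed during the first cycle) with the 28 days in Sections 6 and 6.1.

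Cost: one or two routine tubes per subject, one contact, and an occasional extra attendance for a repeat test.
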